8.2 Lenalidomide

A new course of treatment may begin on the scheduled Day 1 of a new cycle if:

- The ANC is $\geq 1,000/\mu$ L;
- The platelet count is $\geq 25,000/\mu$ L;
- Any lenalidomide-related allergic reaction/hypersensitivity or sinus bradycardia/ other cardiac arrhythmia adverse event that may have occurred has resolved to ≤ grade 1 severity;
- Any other lenalidomide-related adverse event that may have occurred has resolved to \leq grade 2 severity.

If these conditions are not met on Day 1 of a new cycle, the subject will be evaluated weekly and a new cycle of lenalidomide will not be initiated until the toxicity has resolved as described above. If lenalidomide dosing was omitted during the previous cycle and was restarted with a one-level dose reduction without requiring an interruption for the remainder of the cycle, then that reduced dose level will be initiated on Day 1 of the new cycle. If lenalidomide dosing was omitted for the remainder of the previous cycle or if the new cycle is delayed due to toxicity newly encountered on the scheduled Day 1, then the new cycle will be started with a one-level dose reduction.

If either drug is discontinued, patient will come off treatment and go to event monitoring.

| → → Use the NCI Common Terminology Criteria for Adverse Events (CTCAE) version 4.0 unless otherwise specified $\leftarrow \leftarrow$ | | | | |
|---|---|--------------|---|--|
| CTCAE System/Organ/Class (SOC) | ADVERSE EVENT | AGENT | ACTION | |
| | BASED ON INTERVAL | ADVERSE E | EVENTS (Days 2-28) | |
| Investigations | Platelet count decreased*: (Platelets < 10,000/mm ³) | | Omit dose. Follow CBC weekly. If thrombocytopenia resolves to ≤ grade 3 restart lenalidomide at the same dose level. | |
| | | | If thrombocytopenia < 10,000/mm³ recurs, reduce dose by one dose level (5 mg) and continue therapy when platelet count ≥ 25,000/mm³. | |
| | Grade 4 Neutrophil count | | • Omit dose. | |
| | decreased* | | • Follow CBC weekly. | |
| | | Lenalidomide | If neutropenia has resolved to ≤ grade 2, resume dose at same level with GCSF support. | |
| Blood and lymphatic | ≥ Grade 3 Febrile | omi | Omit dose. | |
| system disorders | neutropenia | de | • Follow CBC weekly. | |
| | | | If neutropenia has resolved to ≤ grade 2, resume dose at same level with GCSF support. | |

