| Cardiac Disorders | Sinus bradycardia/ other cardiac Arrhythmia Grade 2 | | Omit dose. Follow at least weekly. If the toxicity resolves to ≤ grade 1, reduce dose by one dose level (5mg) and continue therapy. | |
| | \geq Grade 3 | | • Discontinue study treatment and go to | |
| Vascular disorders | thromboembolic event \geq Grade 3 | | event monitoring. Omit dose and start anticoagulation; restart at investigator's discretion (maintain dose level). | |

| \rightarrow \rightarrow Use the NCI Common Terminology Criteria for Adverse Events (CTCAE) version 4.0 unless | | | |
|---|--|--------------------------|--|
| | otherwise | e specified \leftarrow | F |
| CTCAE System/Organ/Class (SOC) | ADVERSE EVENT | AGENT | ACTION |
| | BASED ON INTERVAL | ADVERSE E | VENTS (Days 2-28) |
| Immune system disorders | Allergic reaction Grade 2-3 | | Omit dose. Follow at least weekly. If the toxicity resolves to ≤ grade 1, reduce dose by 5 mg and continue therapy. |
| Anaphylaxis Grade 4 | | | • Discontinue study treatment and go to event monitoring. |
| | Erythema multiforme ≥ Grade 3 | Г | • Discontinue study treatment and go to event monitoring. |
| Skin and | Skin ulceration \geq Grade 2 | Lenalidomide | • Discontinue study treatment and go to event monitoring. |
| subcutaneous tissue disorders | Other: Non-blistering rash Grade 3 | | If Grade 3 omit dose. Follow weekly. If the toxicity resolves to ≤ grade 2 continue therapy. |
| | Other: Non-blistering rash Grade 4 | | • Discontinue study treatment and go to event monitoring. |
| Other | Non-hematologic toxicity assessed as lenalidomide related ≥ Grade 3 | | Omit dose. Follow at least weekly. If the toxicity resolves to ≤ grade 2, implement one dose reduction step and continue therapy. |

* use IWCLL/Hallek, December 2008 criteria (see Appendix V)

NOTE: Subjects who cannot tolerate the minimum dose 5 mg daily on days 1 - 21 of a 28 day cycle, are to be discontinued from the treatment phase of the study and go to event monitoring.

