Note: Dose modification schedule as outlined in the table above will be applicable to all patients enrolled on the study. This schedule will not be applicable to patients during the two cycles of the combination therapy of the patients enrolled on the phase I portion of the study to clearly define MTD. Once patients on the phase I portion of the study have completed cycle #2 (1st combination cycle) they may be managed based on the dose modification criteria outlined in the table above. Dose modification due to toxicity will be based on dose de-escalation in 5 mg increments from the maximum dose obtained for the individual patient. The optimum dose in any individual patient may be determined by the investigator based on managing toxicity and maximizing response. The maximum dose of lenalidomide permitted will not exceed the MTD determined in the phase I portion of the study and is not to exceed 20 mg daily on days 1 - 21 of a 28 day cycle and the minimum dose permitted is 5 mg daily on days 1 - 21 of a 28 day cycle.

Dose re-escalation: For patients who are dose reduced either for disease or drug related toxicities, lenalidomide dose re-escalation can be considered provided all toxicity has resolved to \leq Grade 1. Patients can be started at minimum of 5mg PO daily on days 1 - 21 of a 28 day cycle and the dose titrated up at 5mg increments weekly to the target dose not to exceed the MTD determined in the phase I portion of the study. The rate of escalation is at the PI discretion based on patient tolerability and concern for tumor lysis syndrome.

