13.0 Treatment/Follow-up Decision at Evaluation of Patient

- 13.1 If the patient develops PD at any time during active treatment, unacceptable adverse events, or patient refuses all further study participation, study treatment will be discontinued and the patient will go directly to event monitoring. Patients will then be followed in event monitoring per Section 18.0.
- 13.2 Patients not progressing on active treatment will continue treatment per protocol up to a maximum of 12 cycles. After the completion of 12 cycles, the patient will go to observation (maximum duration of observation 2 years).
- 13.3 Phase I Only: If a patient fails to complete the first two cycles of treatment for reasons other than toxicity, the patient will be regarded as inevaluable and will be replaced.
- 13.4 A patient is deemed ineligible if after registration, it is determined that at the time of registration, the patient did not satisfy each and every eligibility criteria for study entry. The patient may continue treatment off-protocol at the discretion of the physician as long as there are no safety concerns, and the patient was properly registered. The patient will go directly to the event-monitoring phase of the study (or off study, if applicable).
 - If the patient received treatment, all data up until the point of confirmation of ineligibility must be submitted. Event monitoring will be required per Section 18.0 of the protocol.
 - If the patient never received treatment, on-study material and the End of Active Treatment/Cancel Notification Form must be submitted. No further data submission is necessary.
- 13.5 A patient is deemed a *major violation*, if protocol requirements regarding treatment in cycle 1 of the initial therapy are severely violated that evaluability for primary end point is questionable. All data up until the point of confirmation of a major violation must be submitted. The patient will go directly to the event-monitoring phase of the study. The patient may continue treatment off-protocol at the discretion of the physician as long as there are no safety concerns, and the patient was properly registered. Event monitoring will be required per Section 18.0 of the protocol.

13.6 A patient is deemed a *cancel* if he/she is removed from the study for any reason before any study treatment is given. On-study material and the End of Active Treatment/Cancel Notification Form must be submitted. No further data submission is necessary.

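### Section 8.2 permanently stops treatment for grade 4 non-blistering rash, but has no row for blistering or exfoliative rash, SJS or TEN, so an uncoded grade 4 case above 5 mg falls to a catch-all that allows restart

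*Combined protocol and SAP*

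**What the plan says.** The skin rows of the section 8.2 action table cover three kinds of event. Erythema multiforme at grade 3 or higher and skin ulceration at grade 2 or higher both lead to discontinuation. Non-blistering rash is omitted and then continued at grade 3, and is discontinued at grade 4 ("Other: Non-blistering rash Grade 4"). The immune-system rows omit lenalidomide for grade 2-3 allergic reaction until grade 1 or below, then reduce by 5 mg. They discontinue for grade 4 anaphylaxis.

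The last row, 'Other', is a catch-all: "Non-hematologic toxicity assessed as lenalidomide related ≥ Grade 3". Its action is to omit the dose, follow at least weekly, and then: "If the toxicity resolves to ≤ grade 2, implement one dose reduction step and continue therapy".

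Further rules bear on restarting:

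- **Minimum dose (8.2).** "Subjects who cannot tolerate the minimum dose 5 mg daily" on the 21-of-28-day schedule leave the treatment phase.
- **Day 1 criteria (8.2).** Allergic reaction or hypersensitivity must be at grade 1 or below. The general bullet ("Any other lenalidomide-related adverse event that may have occurred has resolved to") asks only for grade 2 or below.
- **Re-escalation (8.2).** After a reduction, "lenalidomide dose re-escalation can be considered provided all toxicity has resolved to" grade 1 or below.
- **Scope (8.2).** For phase I patients, "This schedule will not be applicable to patients during the two cycles of the combination therapy". The text that follows applies the table once cycle 2, the first combination cycle, is complete.
- **Section 13.1.** Study treatment is to be discontinued for PD, "unacceptable adverse events, or patient refuses all further study participation". The term for the adverse events is not defined.

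Section 15.17 lists SJS and TEN among the rare (below 1%) lenalidomide toxicities that are important or life-threatening.

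**The concern.** Limiting the rash rows to the non-blistering form implies that the blistering form is handled elsewhere, and one would expect at least as strictly. No row does so. A patient with a life-threatening blistering or exfoliative reaction could then meet a written instruction that provides for restart at a lower dose, while a patient with a grade 4 non-blistering rash is taken off treatment. What is at stake is individual safety, namely re-exposure to the suspected drug. The response endpoint, error rates and sample size are not affected.

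The protocol recognises the hazard in section 15.17 and in the nursing guidance at 15.194. Exclusion 3.26 also bars entry after erythema nodosum with a desquamating rash on thalidomide-type drugs. That criterion governs entry only and sets no on-study rule. It shows that severe skin reactions to this drug class were in view.

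**Working it through.** The first step is to trace each lenalidomide-related event through the table at a dose above 5 mg.

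| Event as coded | Row that applies | Restart provided for? |
|---|---|---|
| Erythema multiforme, grade 3 or higher | Own row | No |
| Skin ulceration, grade 2 or higher | Own row | No |
| Non-blistering rash, grade 3 | Own row | Yes, at grade 2 or below; no reduction stated |
| Non-blistering rash, grade 4 | Own row | No |
| Allergic reaction, grade 2-3 | Own row | Yes, at grade 1 or below, 5 mg lower |
| Anaphylaxis, grade 4 | Own row | No |
| Blistering or exfoliative rash, SJS or TEN, grade 3, not coded as above | 'Other' | Yes, at grade 2 or below, one step lower |
| The same, grade 4 | 'Other' | Yes, at grade 2 or below, one step lower |

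Three limits follow.

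1. **Grade.** The inversion is at grade 4 only. At grade 3 the catch-all is the stricter row, because it adds a dose reduction.
2. **Dose.** At 5 mg there is no lower step, and the minimum-dose note leads off treatment.
3. **Period.** The table is suspended for phase I patients in the MTD-defining combination period.

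The second step is to see whether a neighbouring rule supplies the missing stop.

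- The Day 1 criteria delay a new cycle until grade 2 or below, or grade 1 or below if the event is classed as allergic reaction or hypersensitivity. They raise the bar but do not prohibit restart.
- The re-escalation rule has no exception for severe skin reactions.
- If the event is attributed to AT-101, section 8.3 also allows resumption at a reduced AT-101 dose.
- Section 15.194 asks patients to report any rash because of SJS and gives no dosing action.
- Expedited reporting (10.4), the cycle 2 DLT rule (7.221) and the accrual-suspension rule (16.52) flag or count the event. None of them decides whether that patient restarts.

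The third step is size. The inputs are dose levels 2 to 4 (10, 15 and 20 mg; section 7.21), a maximum of 6 patients per level (16.21 to 16.224), at most 31 additional evaluable phase II patients (16.12), and the below-1% heading (15.17).

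- Maximum evaluable patients starting above 5 mg: 3 × 6 + 31 = 18 + 31 = 49.
- Expected SJS/TEN cases of any grade at the 1% ceiling: 49 × 0.01 = 0.49, so fewer than 0.49.
- At an assumed rate of 0.1%: 49 × 0.001 = 0.049, about 0.05.

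The ceiling does not fall in simple steps with the MTD. Sections 16.222 and 16.224 escalate after 0 of 3 and later backfill a lower level to 6. That level can then fail in turn, so levels 2 to 4 can each hold 6 patients even when the MTD ends lower. With an MTD of 10 mg the ceiling is still 18 + 31 = 49. With the MTD at level 1 it is 18, since phase II then runs at 5 mg. Below level 1 it is not zero, because level 2 can be treated before level 1 is expanded and fails.

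**The case against.** The strongest reply has three parts.

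First, the gap opens only if the event escapes every stopping row, and coding follows CTCAE v4.0. Neither that document nor the package insert cited in 15.17 is available here. Real SJS or TEN cases might be coded as erythema multiforme or skin ulceration, both of which stop treatment below grade 4. This stands as a limit on frequency: the documents do not show how often a case would escape. It does not supply the missing row, and whether a patient is re-exposed should not turn on the choice of term.

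Second, section 13.1 makes stopping mandatory for unacceptable adverse events, section 8.2 lets the investigator set the individual dose, and re-escalation is only optional. Most investigators would presumably not rechallenge after SJS or TEN. That is fair. But 13.1 leaves its trigger undefined and does not say that it overrides the specific instruction in the 'Other' row.

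Third, the event is very rare, and nothing in the analysis changes. This stands, and it sets the severity.

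A reader might go further and infer that the protocol requires rechallenge after SJS or TEN, that it overlooked the risk, or that it is laxer for blistering rash at every grade. The documents do not support any of these. Section 13.1 allows a stop at any time, 15.17 and 15.194 name the risk, and at grade 3 the catch-all is stricter than the non-blistering row.

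**Conclusion.** The concern holds in a narrow form and is minor. For a lenalidomide-related grade 4 blistering, desquamating or exfoliative reaction, SJS or TEN, above 5 mg, outside the phase I MTD-defining combination period and not coded to a stopping row, the written rule is less safe than the rule for grade 4 non-blistering rash. It allows restart one step lower at grade 2 or below, and re-escalation can be considered at grade 1 or below.

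The size rests on three assumptions. The 15.17 heading is read as a 1% ceiling on SJS and TEN taken together. The 0.1% rate is illustrative and is not given in the documents. The documents give no separate rate for other blistering or exfoliative rashes, so these are not in the count. On that basis fewer than 0.49 cases of any grade are expected among at most 49 patients. Grade 4 SJS/TEN cases that escape the stopping rows and are then restarted would be fewer still. Confidence is medium, because likely coding cannot be checked from the documents.

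**What to change.** Add one row to the skin section of the 8.2 table: discontinue study treatment and go to event monitoring for grade 4 blistering, desquamating or exfoliative rash, and for suspected SJS or TEN. Exclude these events from the 'Other' row and from the dose re-escalation rule, so that no other text in 8.2 reopens the restart route.

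The change is one row and two short exclusions in an amendment, with no effect on sample size, endpoints or analysis. Its downside is that a rare patient who might have tolerated a lower dose comes off treatment. The table already accepts that cost for grade 4 non-blistering rash.

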We also conducted *in vitro* studies of AT-101 and observed its ability to induce apoptosis in B-CLL cells. Thus, AT-101 is a novel, oral agent with ability to target Bcl-2 family of antiapoptotic protein that has demonstrated *in vitro* and in patient anti-CLL activity. Collectively the pre-clinical and clinical data available and presented here and the data available on Lenalidomide allow us to put forward the following hypothesis: **Hypothesis:** Concurrent targeting of B-CLL cell microenvironment by lenalidomide and the tumor cell itself by AT-101 will result in an enhanced antileukemic effect (**Fig 4**). Therefore we propose to conduct a phase I/II clinical trial to first determine the maximum

tolerated dose of fixed dose of AT-101 in combination with escalating doses of Lenalidomide and subsequently investigate the clinical efficacy of this combination.

Rationale for the combination and dosing:

Developing a novel regimen for relapsed /refractory B-CLL patients is an unmet need. AT-101 and lenalidomide have been tested in phase II studies independently and have

demonstrated anti-leukemic potential. Despite encouraging results most patients only achieved partial remission with single agent use of these agents. There are several important reasons that rationalize to develop the combination of lenalidomide with AT-101 these are; (1) both have clinically active in patients with B-CLL (2) They have non overlapping toxicities (major toxicity for lenalidomide is hematologic while that for AT-101 is gastrointestinal) (3) both an be delivered orally and are patient convenient (4) Both have mutually exclusive targets (lenalidomide targets the microenvironment and results in immune activation while AT-101 down regulates the prosurvival signals of Bcl-2 family of proteins i.e., Bcl-2, Mcl-1 resulting in enhanced susceptibility to undergo apoptosis).

We will initiate lenalidomide at 5mg per day, while using the sample 21 out of 28 day cycle schedule as published previously. This is the minimum dose at we were able to demonstrate antileukemic effects of lenalidomide. The dose of lenalidomide will be escalated over 4 cohorts as outlined later in the study protocol. Although the administered dose in our previous study was 25mg / day the most tolerable dose (in terms of hematologic) was 20mg / day. Therefore in this study we propose that the maximum dose to be investigated in combination with AT-101 be 20mg/day.

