8.0 Dosage Modification Based on Adverse Events

8.1 Dose Levels (Based on Adverse Events in Tables 8.2 and 8.3)

* Dose level 1 refers to the starting dose.

Omit = The current dose(s) for the specified drug(s) during a cycle is skipped. The patient does not make up the omitted dose(s) at a later time

Hold/Delay = The current dose(s) of all drugs during a cycle is delayed. The patient does make up the delayed dose(s) when the patient meets the protocol criteria to restart drugs.

Discontinue = The specified drug(s) are totally stopped.

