8.3 AT-101

During the study period it is the goal to prescribe the fully intended dose of AT-101. It is expected that toxicity of AT-101 can be solved with appropriate measures. However, in case of severe toxicity (grade \geq 3) attributed (possibly, probably or definitively) to AT-101, treatment will be held for a maximum of 8 weeks. If toxicities resolve to \leq grade 1, patients may resume treatment. Patients who are resumed on treatment will be started at a lower dose of AT-101 (25% dose reduction or 30mg BID); if the toxicity recurs (grade \geq 3) then one more dose reduction (50% dose reduction or 20mg BID) will be allowed (upon resolution of toxicity \leq grade 2). If toxicity recurs \geq grade 3, patients will be removed from the study treatment and go to event monitoring.

Note: No dose reduction is allowed in cycle #2 as this is the MTD defining cycle.

| \rightarrow \rightarrow Use the NCI Common Terminology Criteria for Adverse Events (CTCAE) version 4.0 unless | | | | | | | |
|---|--|-----------|--|--|--|--|--|
| otherwise specified $\leftarrow \leftarrow$ | | | | | | | |
| CTCAE System/Organ/Class (SOC) | ADVERSE EVENT | AGENT | ACTION | | | | |
| BASED ON INTERVAL ADVERSE EVENTS (Days 2-3) | | | | | | | |
| Gastrointestinal disorders | BASED ON INTERVAL ≥ Grade 2 Nausea ≥ Grade 2 Vomiting Any Grade Abdominal pain | ADVERSE E | For any of these events that last longer than 48 hours, AT-101 should be omitted and the following actions are recommended: Physical examination, including assessment of vital signs Screening abdominal radiography to include an abdominal series to exclude ileus, small bowel obstruction (SBO), or pneumatosis intestinalis. Consideration for obtaining a CT scan with contrast of the abdomen should be made based on clinical judgment If ileus, non-mechanical SBO, or pneumatosis intestinalis are excluded, AT-101 dosing may be reinstated. If a patient is determined to have ileus, SBO, or pneumatosis intestinalis, AT- | | | | |
| | | | 101 dosing should be permanently discontinued and expectant management with supportive care is recommended, unless clinical signs or symptoms are present that suggest | | | | |
| | | | septicemia or abdominal catastrophe that warrants surgical management. | | | | |

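### The phase I exemption in the 8.2 note has two conflicting windows and, as worded, suspends the whole lenalidomide table in cycle 2 instead of only its dose reductions

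*Combined protocol and SAP*

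**What the plan says.** The note to the lenalidomide table in Section 8.2 first applies the table to every patient. It then makes an exception for phase I, so that the MTD can be clearly defined: "This schedule will not be applicable to patients during the two cycles of the combination therapy". The next sentence says that once phase I patients "have completed cycle #2 (1st combination cycle) they may be managed based on the dose modification criteria outlined in the table above".

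The corresponding note for AT-101 in Section 8.3 is narrower: "No dose reduction is allowed in cycle #2 as this is the MTD defining cycle". The AT-101 hold rule stays in force. For grade 3 or higher toxicity "attributed (possibly, probably or definitively) to AT-101, treatment will be held for a maximum of 8 weeks". Section 8.1 defines the terms: "Hold/Delay = The current dose(s) of all drugs during a cycle is delayed", and "Discontinue = The specified drug(s) are totally stopped".

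**The concern.** Two things look wrong. The note gives two end points for one exemption. It also exempts phase I patients from the table as a whole, although the purpose of protecting the MTD cycle needs only a bar on dose reductions, which is all that 8.3 imposes.

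The table holds the event-specific instructions for omitting or stopping lenalidomide. Followed literally, the note removes them in the first cycle in which the two drugs are given together, the cycle with the least prior experience. Two investigators could manage the same patient differently and each cite the protocol. One of these differences can reach the phase I endpoint, through the neutrophil DLT criterion.

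**Working it through.** The plan states no figure on this point to reproduce. The check compares sections and counts table rows.

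**1. Window.** Under 7.11, cycle 1 is lenalidomide alone and AT-101 is added from cycle 2. Two combination cycles are therefore cycles 2 and 3. The note's second sentence ends the exemption when cycle 2 is complete. The two statements differ by cycle 3, which is 28 days (7.1). Other sections point to cycle 2 only:
- 7.212 observes the first combination cycle, to day 28.
- 7.221 counts DLTs in cycle 2.
- The 8.3 note calls cycle 2 the MTD-defining cycle.
- 9.2 bars growth factors in cycle 2 of phase I.
- 16.226 counts one lenalidomide cycle and one combination cycle as the first two.

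If the note meant treatment cycles 1 and 2, the end points would agree. But cycle 1 is not combination therapy, and it would then be exempt as well.

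**2. Scope.** The 8.2 table has 13 rows.
- Omit first (8): platelets below 10,000; grade 4 neutropenia; febrile neutropenia; grade 2 arrhythmia; thromboembolic event; grade 2-3 allergic reaction; grade 3 rash; other grade 3 or higher non-hematologic toxicity.
- Discontinue (5): grade 3 or higher arrhythmia; grade 4 anaphylaxis; grade 3 or higher erythema multiforme; grade 2 or higher skin ulceration; grade 4 rash.
- Check: 8 + 5 = 13.
- Rows containing a reduction (4, all among the omit rows): platelets on recurrence; grade 2 arrhythmia; allergic reaction; other grade 3 or higher.

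A bar on reductions alone would touch 4 rows. The note as worded suspends 13.

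**3. What still applies in phase I cycle 2.**

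| Provision | What it does | Limit |
|---|---|---|
| 8.2 Day 1 criteria | Graded and lenalidomide-specific; gate each new cycle | Act at cycle start, not mid-cycle |
| 8.2 note on the minimum dose | Stops patients who cannot tolerate 5 mg | Names no event or grade |
| 8.3 hold | Delays all drugs, by the 8.1 definition | Needs grade 3 or higher, at least possibly due to AT-101 |
| 9.6 | Stops treatment for grade 4 tumor flare | That event only |
| 9.8 | Holds treatment for DVT/PE | That event only |
| 7.213 | Study Chair contacted for any DLT | Does not itself stop drug |
| 13.1 | Stops treatment for unacceptable events | No grade; a judgment |

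**4. Rows against backstops.** Three rows include grade 2 events (arrhythmia, allergic reaction, skin ulceration), which the 8.3 hold does not reach. One row, thromboembolism, has its own hold in 9.8. The other 13 - 3 - 1 = 9 rows are grade 3 or higher events, which 8.3 holds only if AT-101 is at least a possible cause. A grade 2 skin ulcer, for which the table stops treatment, even passes the general Day 1 criterion of grade 2 or lower.

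**5. Link to the DLT definition.** One criterion in 7.221 depends on duration: ANC at or below 0.5 x 10^9/L for more than 14 days. Section 15.191 says that myelosuppression reverses with interruption, so omitting or continuing lenalidomide could change whether the criterion is met. The 8.3 hold is an unlikely route here, because Section 1.0 says that the "major toxicity for lenalidomide is hematologic while that for AT-101 is gastrointestinal". Febrile neutropenia is a DLT at any duration, so this duration question does not arise for it. In cohorts of three, one DLT triggers expansion and two of six exceed the MTD (16.223), so one patient's classification can matter.

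**The case against.** The best case for the plan is that the note is loose wording with an obvious meaning. It says that modification for toxicity is by de-escalation in 5 mg steps, and its stated purpose is to define the MTD. Both fit a reductions-only reading that matches 8.3. The window clash is easily resolved, since every other section points to cycle 2. Several protections lie outside the table. This is largely right about intent, and it limits the size of the problem. It does not supply the missing mid-cycle actions.

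A reader might go further in four ways that the documents do not support.
- **That phase I patients must be dosed through severe toxicity.** Section 13.1 requires stopping for unacceptable events, 7.213 requires prompt contact for a DLT, and 13.3 and 16.226 expect that some patients will not complete cycle 2 because of toxicity.
- **That no graded lenalidomide rule survives.** The Day 1 criteria in 8.2 are graded, specific to lenalidomide and outside the table. They also gate entry to cycle 3.
- **That 8.3 lets a patient whom the table would discontinue restart within cycle 2.** It does say that "patients may resume treatment" after resolution, but at a lower AT-101 dose, and the 8.3 note bars reductions in that cycle.
- **That the MTD is biased by a known amount.** The documents give no frequency for prolonged neutropenia. The extra cycle in the wider window falls outside DLT counting.

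**Conclusion.** Wrong as written, and it should be corrected. The two windows conflict over cycle 3, a matter of toxicity handling only. The scope of the exemption matters more: all 13 rows are suspended where a bar on reductions would touch 4.

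The remaining gap in cycle 2 is a mid-cycle, event-specific lenalidomide action for grade 2 arrhythmia, allergic reaction or skin ulceration and, outside 9.6 and 9.8, for grade 3 or higher toxicity attributed to lenalidomide alone. The action at grade 4 neutropenia is unclear, with a possible but unquantified effect on the ANC-duration DLT criterion.

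This rests on reading the exempted schedule as the table that the note itself refers to. On a reductions-only reading the safety gap closes, but the text does not say that.

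**What to change.** State in 8.2 that, for phase I patients:
- the exemption covers cycle 2 only and bars only lenalidomide dose reductions;
- omit, hold and discontinue actions stay in force;
- any restart in cycle 2 after neutropenia is without G-CSF, because the table's restart with G-CSF conflicts with 7.11 and 9.2;
- where the table requires a reduction to restart (grade 2 arrhythmia, grade 2-3 allergic reaction, other grade 3 or higher non-hematologic toxicity, recurrent platelets below 10,000), lenalidomide waits until cycle 3;
- an omission for a non-DLT event does, or does not, count as completing cycle 2 under 16.226. Section 13.3 exempts any toxicity from replacement while 16.226 exempts only DLT-defined events, so the two should be aligned.

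The cost is a few sentences. Sample size, decision rules and analyses do not change. The one consequence to settle is the last item, because it decides which patients are replaced.
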